#### **4.1.7.2 Presentation**

Data for each Substudy will be presented as per Section [3.3.](#)

Medical history, concomitant disease and surgical history are summarised for the safety analysis set by System Organ Class (SOC) and Preferred Term (PT).

Summaries on participants' medical history by system organ class and preferred term are produced.

### **Previous Cancer Therapy**

Summaries of the number and percentage of participants who have had previous cancer treatments are provided by therapeutic class and Anatomical Therapeutic Chemical (ATC) classification and generic drug name for the safety analysis set. The number of regimens of previous anti-cancer therapies at baseline and best response in most recent regimen are summarised as a continuous and categorical variables. Previous treatments are summarised by number of regimens. Previous disease related chemotherapy treatments are summarised by number of regimens, type of treatment and modality. Additionally, the following

characteristics are summarised for previous treatments: generic name, time since last dose, treatment status, treatment duration, best response, reason for therapy failure and platinum sensitivity status at study entry.

### **Previous Radiotherapy**

Summaries of the number and percentage of participants who had at least 1 prior radiotherapy are presented for the safety analysis set. Details on previous radiotherapy are listed.

### **Previous immunotherapy:**

Summary statistics are presented for time from the last immunotherapy treatment to first IP dose (days) and duration of last prior immunotherapy treatment (days). This information will also be presented for immediate immunotherapy, including only patients for whom the last therapy they had prior to study IP was immunotherapy. Summary statistics are presented for the length all immunotherapy treatments.

## **4.1.8 Prior and Concomitant Medications**

### **4.1.8.1 Definitions and Derivations**

For the purpose of inclusion in prior and/or concomitant medication or therapy summaries, incomplete medication or radiotherapy start and stop dates are imputed as detailed in Section [3.3.6](#).

Prior medications, concomitant medications and post medications are defined based on imputed start and stop dates as follows:

- Prior medications are those taken prior to IP with a stop date prior to the first dose of IP.
- Concomitant medications are those with a stop date on or after the first dose date of IP and must have started prior to or during treatment so there is at least one day in common with the IP.
- Post-treatment medication are those with a start date after the last dose of IP

### **4.1.8.2 Presentation**

The number and percentage of participants who took prior, concomitant medications, or post treatment medications are summarised and listed for the safety analysis set by ATC code and the generic name/term coded by the World Health Organization Drug Dictionary (WHODrug). Concomitant medications include all concomitant medications taken on or after the date of first dose of study treatment or any concomitant medication started prior to the first dose of study treatment that continued beyond the date of first dose of study treatment.

The number and percentage of participants who have had post-treatment medications, therapy class and agents received are summarised, this includes the number of participants

who have had subsequent anti-cancer therapies, and the best response from subsequent therapy.

### Metformin

The number and percentage of participants who took Metformin medication prior to IP treatment are summarised separately if data allows (i.e., more than 5 participants took Metformin treatment), else data are only listed. The time between last dose of Metformin and first dose of IP treatment are also summarised, and can be calculated by the below formula:

Time since last Metformin dose (days)=  
(Date of first dose of IP-Date of last Metformin dose + 1)

Data for each Substudy will be presented as per Section [3.3.](#)

## 4.2 Endpoint Analyses

This section covers details related to the endpoint analyses such as primary, secondary, and other endpoints including sensitivity and supportive analyses. Core endpoint analyses are described in [Table 3](#).

Endpoints that are specific to ‘Substudy 1’ are provided in [Table 4](#). Exploratory analyses for Substudy 1 will be reported separately from the CSR and therefore will be described outside of the SAP.

**Table 3: Core Endpoint analysis**

Statistical category	Endpoint	Population	Population level summary (analysis)	Details in section
Objective 1: To assess safety and tolerability, characterize DLTs (in dose escalation parts only) and determine the MTD or RP2D of AZD8853 in participants with selected advanced/metastatic solid tumours				
Primary	AEs, SAEs, clinically significant changes from baseline in clinical laboratory parameters, vital signs, and ECG results, Incidence of AEs leading to discontinuation of AZD8853.	Safety analysis set	Percentage of participants with AEs, SAEs, clinically significant changes from baseline in clinical laboratory parameters, vital signs, and ECG results. Percentages of participants with AE leading to discontinuation	4.2.1
Objective 2: To determine the preliminary anti-tumour activity of AZD8853 in participants with selected advanced/metastatic solid tumours				

Statistical category	Endpoint	Population	Population level summary (analysis)	Details in section
Secondary	ORR according to RECIST v 1.1	Response evaluable set	Rate and 90% CI (2-sided CI)	4.2.2
Secondary	DCR at Week 15 according to RECIST v 1.1	Response evaluable set	Rate and 90% CI (2-sided CI) for each cohort at 15 weeks.	4.2.4
Secondary	DoR according to RECIST v 1.1	Subset of response evaluable set: participants with confirmed objective response	Kaplan-Meier plots and median DoR time estimated using Kaplan Meier method.	4.2.5
Secondary	PFS	Safety analysis set	Kaplan-Meier plots and median PFS time estimated using Kaplan Meier method.	4.2.6
Secondary	Change in target lesion tumour size	Response evaluable set	Percentage change in tumour size from baseline, at each timepoint is summarized by mean change and St Dev  Percentage change from baseline for each participant is produced over time in a spider plot.  Waterfall plots of percentage change from baseline and best percentage change from baseline is produced.	4.2.7
Secondary	OS	Safety analysis set	Kaplan-Meier plots and median OS time estimated using Kaplan Meier method.	4.2.8
Objective 3: To assess the efficacy of AZD8853 using longitudinal blood samples in participants with selected advanced/metastatic solid tumours				
Secondary	Change in ctDNA from baseline	Safety analysis set	Percentage change in ctDNA from baseline to each post baseline timepoint is summarized by mean change and St Dev. Maximum change is	4.2.9

Statistical category	Endpoint	Population	Population level summary (analysis)	Details in section
			also summarised by mean and St. Dev.	
Objective 4: To determine the PK of AZD8853 in serum when administered in participants with selected advanced/metastatic solid tumours				
Secondary	PK parameters (include but not limited to Cmax and AUC)	PK analysis set	Summary of PK profile of AZD8853	4.2.12
Objective 5: To assess the immunogenicity of AZD8853 in participants with selected advanced/metastatic solid tumours				
Secondary	ADAs against AZD8853 in Serum	Immunogenicity analysis set	Incidence of detectable ADAs against AZD8853 in serum	4.2.13

ADA = antidrug antibodies; AUC = Area Under the Curve; AEs = Adverse Events; CI= Confidence Interval; ctDNA = circulating tumour deoxyribonucleic acid; DCR= disease control rate; DLT= dose limiting toxicity; DoR=duration of response; ECG= Electrocardiogram; MTD = Maximum Tolerated Dose; OS= overall survival; ORR=objective response rate; PFS=Progression Free Survival; PK =pharmacokinetics; RECIST = Response Evaluation Criteria in Solid Tumours v1.1; RP2D = Recommended Phase 2 Dose; SAEs = Serious Adverse Events; St. Dev = Standard Deviation.

**Table 4: Substudy 1 Endpoints**

Statistical category	Endpoint	Population	Population level summary (analysis)	Details in section
Objective 1: To assess safety and tolerability, characterize DLTs (in dose escalation parts only) and determine the MTD or RP2D of AZD8853 in participants with selected advanced/metastatic solid tumours.				
Primary (Part A only)	DLTs	DLT evaluable set	Number of participants with DLTs.	4.2.1.8
Objective 6: To evaluate the PD activity of AZD8853 by assessment of candidate biomarkers in participants with selected advanced/metastatic solid tumours (Part A and Part B only)				
Secondary	Change in circulating GDF15 serum levels	PD analysis set	Actual and percentage change in circulating GDF15 serum levels from pre-treatment (baseline) to each post baseline timepoints as well as the maximum change will be summarised using descriptive statistics such as mean change and St.Dev.	4.2.10

Statistical category	Endpoint	Population	Population level summary (analysis)	Details in section
Objective 7: To evaluate the intra-tumoral PD activity of AZD8853 in participants with selected advanced/metastatic solid tumours (Part B only)				
Secondary	Change in CD8 tumour infiltration by IHC using baseline and on-treatment samples	Subset of PD analysis set (who have paired biopsies)	Change in CD8 tumour infiltration by IHC between the pre-treatment and on-treatment biopsy will be summarised using descriptive statistics such as mean change and St.Dev.	4.2.11

BMI=Body Mass Index; CD8=cluster of differentiation 8; DoR=duration of response; DNA= Deoxyribonucleic acid; IHC=Immunohistochemistry; **CCI** ; OS= overall survival; ORR= objective response rate; PD=pharmacodynamics; PFS= Progression Free Survival; PK=pharmacokinetics; PET= positron emission tomography; RNA = Ribonucleic acid; SAP = Statistical Analysis Plan; St. Dev = Standard Deviation; SMI= Skeletal muscle index; SUV = Standardized Update Value.

Efficacy analyses, except for OS and ctDNA, are based on programmatic application of Response Evaluation Criteria in Solid Tumours (RECIST) v1.1 (Eisenhauer et al, 2009) to investigator assessed tumour measurements. Programmatic derivation guidance used for the application of RECIST v1.1 are provided in Appendix A in the [Appendices](#), which is used to determine disease response. RECIST v1.1 data with overall visit response and best objective response are listed.

RECIST v1.1 data, overall visit response and best objective response are listed. Additional listing(s) are produced for tumour assessments per patient, BOR, DOR, DCR.

## Substudy 1

For Substudy 1, all efficacy analyses are presented separately for part A, B and C. For part A data is presented by dose level and overall. For part B, data is presented in separate tables for tumour type by dose level and overall. For part C, data is presented in separate tables for indication by dose level (as applicable at the time). Safety data will be presented as follows:

- Part A only - during dose escalation.
- Part B only (by tumour type)
- Part A+B+C if patients have the same dose and same disease
- Part C only (by indication)

#### 4.2.1 Safety

The Safety and tolerability primary endpoints are assessed in terms of AEs/ Serious Adverse Events (SAEs), AEs leading to discontinuation of AZD8853, DLTs, clinically significant changes from baseline in clinical laboratory parameters, vital signs, and electrocardiogram (ECG) results.

The domain safety also covers exposure and ECOGs.

These variables are collected for all participants. All safety analyses are performed on the safety analysis set. Listings are provided for all participants or the safety analysis set depending on the availability of data.

DLT summaries or listings are provided on the DLT evaluable population set.

##### 4.2.1.1 Exposure

###### 4.2.1.1.1 Definitions and Derivations

Infusion administered medications

###### Substudy 1:

- Duration of exposure is defined by last date of actual dosing (i.e., a dose  $> 0$  [mg] is given) in the last cycle plus 21 days minus the date of first treatment with IP plus 1 day.
  - For participants who die whilst on study treatment or if a DCO occurs, duration of exposure is defined as date of death/DCO (whichever occurs first) minus the date of first treatment plus 1 day.
  - Therefore: Duration of exposure(days) = (min (last dose date where dose  $> 0$  [mg] + 21 days, date of death, date of DCO) – first dose date + 1).
- The duration of exposure in cycles is calculated as:

Duration of exposure (cycles)= The number of cycles in which at least one portion of IP was administered (i.e., dose  $> 0$  [mg])

If a cycle is prolonged due to toxicity, this should still be counted as one cycle.

- The actual duration of exposure is calculated as:

Actual duration of exposure

(days)= Number of cycles participants received X 21 (days)

Duration of exposure is calculated as above, and dose interruptions are defined as any length of time where the participant has not taken any of the planned dose in accordance

with the protocol. The actual exposure calculation makes no adjustment for any dose reductions that may have occurred.

- Dose intensity of IP(s) is addressed by considering relative dose intensity (RDI), where RDI is the percentage of the actual dose delivered relative to the intended dose through to treatment discontinuation. More specifically, RDI is defined as follows:

$$RDI = 100 \times d/D$$

- where d is the actual cumulative dose delivered up to the actual last day of dosing and D is the intended cumulative dose up to the actual last day of dosing. D is the total dose that would be delivered if there were no modification to dose or schedule.
- Percentage of first dose received, which is used to define the DLT population is calculated as

$$\text{Percentage of dosing received} = \frac{\text{Actual first dose of AZD8853 received}}{\text{Planned first dose of AZD8853 received}} * 100$$

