10.4 Substudy 1 Study Design

10.4.1 Substudy 1 Design

In this Substudy of the FTiH, open-label, multicentre study, AZD8853 will be evaluated as monotherapy for safety, PK, PD, and preliminary efficacy in participants with selected advanced/metastatic solid tumours defined as:

- Second or later line setting of unresectable, locally advanced (Stage III) or metastatic (Stage IV) NSCLC that have progressed on anti-PD-1/PD-L1 inhibitors with or without platinum-containing chemotherapy.
- Third or later line setting of Stage IV MSS-CRC that have progressed on prior standard of care treatment.
- Second or later line setting of Stage IV UC that have progressed on prior treatment with platinum and/or checkpoint inhibitors.

The tumour types included in this study were selected based on unmet clinical need and underlying tumour biology. In both the dose-escalation (Part A) and dose-expansion (Parts B and C) parts of the study, participants with selected advanced/metastatic solid tumours who have progressed or are refractory to at least one line of standard therapy will be enrolled. These populations are thought to represent an unmet clinical need as currently available treatment options provide limited benefit. Moreover, internal investigation has revealed that NSCLC, MSS-CRC, and UC participants exhibit significantly higher serum GDF15 levels when compared to aged matched controls, and that higher serum GDF15 is correlated with a reduced overall survival (Mehta et al, 2015; Arfsten et al, 2019; and Traeger et al, 2019).

Participants will be followed until either death, loss to follow-up, withdrawal of consent or end of study. This Substudy of the study will comprise of 3 main parts (Figure 3), as follows:

Part A: Dose Escalation

The dose-escalation part of the study may enrol up to 45 participants (assuming up to 5 dosing cohorts and 3-9 participants per cohort) with selected advanced/metastatic solid tumours (NSCLC, MSS-CRC and UC). AZD8853 will be administered as monotherapy at the selected dose by i.v. infusion on a Q3W schedule. All participants will be treated until progressive disease, unacceptable toxicity, or withdrawal of consent.

See Section 10.6.6.1 for the starting dose, dose escalation and stopping criteria.

Part B: PD/MoA Expansion

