10.6.8 Definition of DLT

Dose limiting toxicity includes event(s) which happen during the 21 days of Cycle 1 of Part A and represent ≥ Grade 3 toxicity, as defined below, which is not clearly attributable to the disease under investigation, other concomitant medications, disease-related processes under investigation, or another non-drug-related aetiology, with modifications or exceptions noted below.

The DLT evaluation period is from the first exposure of AZD8853 until the end of Cycle 1, which is 21 days. All DLTs must be documented as AEs, graded according to

NCI CTCAE v5.0 and need to be followed until improvement to CTCAE Grade < 1. A minimum of at least 3 DLT-evaluable participants are required for the SRC to hold a dose-escalation vote.

An AE not listed below, or an AE meeting the DLT criteria below but occurring outside of the DLT period may be defined as a DLT-like event after consultation with the Sponsor and Investigators based on the emerging safety profile.

The following toxicities constitute a DLT:

- Any death not clearly due to the underlying disease or extraneous causes.
- Grade 4 adverse events of immune nature (imAE).
- Any ≥ Grade 3 non-infectious pneumonitis regardless of duration; diagnosis should include clinical evaluation, monitoring of oxygenation using pulse oximetry (resting and exertion), laboratory workup and high-resolution CT scan.
- Any \geq Grade 3 non-infectious colitis irrespective of duration after confirmation by colonoscopy and histopathology.
- Any Grade 3 imAE, including rash, pruritus, or diarrhoea (NOTE: this excludes colitis or pneumonitis, as these AEs are already defined above), that does not downgrade to Grade ≤ 2 within 7 days after onset of the event despite maximal supportive care including systemic corticosteroids.
- Liver transaminase elevation:
 - i. Criteria for all participants except participants with elevated transaminases (ALT/AST) at baseline/screening due to liver metastasis:
 - Isolated liver transaminase elevation $> 5 \times \text{but} \le 8 \times \text{ULN}$ that does not downgrade to AST/ALT $\le 3 \times \text{ULN}$ within 14 days after onset with optimal medical management.
 - Isolated liver transaminase elevation > 8 × ULN regardless of duration or reversibility.

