From study day 351 (study week 51 onwards [when the scheduling changes to twelve-weekly assessments]), two missed visits equate to 26 weeks (i.e.  $2 \times 12 \text{ weeks} + 1 \text{ week for an early assessment} + 1 \text{ week for a late assessment} = 26 \text{ weeks}$ ). This is also summarised in the [Table 8](#) below.

Where study day, is the number of days on the study, in which Cycle 1 Day 1 is taken as study day 1.

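### The SAP's duration of exposure counts one day too many, and actual duration is not cut at death or data cut-off although total duration is

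*SAP*

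**What the plan says.** SAP 4.2.1.1.1 (Exposure, Definitions and Derivations, Substudy 1) defines three durations.

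- **Total duration in days.** The last date of a non-zero dose "in the last cycle plus 21 days minus the date of first treatment with IP plus 1 day". For a death on treatment, or when a DCO occurs, "duration of exposure is defined as date of death/DCO (whichever occurs first) minus the date of first treatment plus 1 day". The closing formula takes the minimum of last dose date + 21, "date of death, date of DCO) – first dose date + 1".
- **Duration in cycles.** The number of cycles in which any IP was given. "If a cycle is prolonged due to toxicity, this should still be counted as one cycle".
- **Actual duration in days.** "Number of cycles participants received X 21 (days"). No minimum with death or DCO is attached to it. The text that follows defines dose interruptions and says that dose reductions are not adjusted for.

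SAP 4.2.1.1.2 plans descriptive statistics and frequencies for duration of exposure in days. It does not name a summary of actual duration. Protocol 9.4.2 also calls for duration of exposure to be summarised.

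**The concern.** There are two separate defects.

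First, with inclusive day counting, a dose covers its own day and the 20 that follow. Adding 21 to the last dose date and then adding 1 counts the first day of the next cycle as well. A participant with no delay, skip or interruption therefore shows a total one day longer than the cycles received.

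Second, total duration stops at death or DCO but actual duration always credits the last cycle with a full 21 days. Actual duration can then include days after the participant has died or after the data end. A measure meant to leave out interruptions should not exceed the elapsed time from which they are left out.

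At stake is whether the exposure figures in the study report are correct and agree with each other.

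**Working it through.** **Inputs**

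- Cycle length 21 days: the DLT period runs "until the end of Cycle 1, which is 21 days" (Protocol 10.6.8).
- Dosing every 3 weeks: "by i.v. infusion on a Q3W schedule" (Protocol 10.4.1).
- Day numbering: study day is counted so "in which Cycle 1 Day 1 is taken as study day 1" (SAP 4.2.6.2, a tumour-assessment section, but the same convention). Protocol Table 13 places C2D1 on Day 22, so cycle 1 is Days 1 to 21.
- The total and actual formulas: SAP 4.2.1.1.1.

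The SAP gives no worked exposure figure. The only benchmark is the 21-day cycle.

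**Step 1: one cycle, no cut.** Total = (1 + 21) − 1 + 1 = 22 days. The benchmark of 21 is not reproduced.

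**Step 2: n on-schedule cycles, no cut.** The last dose is on day 1 + 21(n − 1), so total = 21(n − 1) + 21 + 1 = 21n + 1.

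| n | Total as written | Actual (21n) | Total with +20 |
|---|---|---|---|
| 1 | 22 | 21 | 21 |
| 2 | 43 | 42 | 42 |
| 4 | 85 | 84 | 84 |
| 6 | 127 | 126 | 126 |

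The relative error is 1/21 = 4.8% at one cycle, 1/42 = 2.4% at two and 1/126 = 0.8% at six.

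**Step 3: death or DCO k days after the last dose, cumulative earlier delay L days, k from 0 to 20.** Total = 21(n − 1) + L + k + 1 and actual = 21n, so actual − total = 20 − k − L. With no delay, actual is the larger for k = 0 to 19, by at most 20 days.

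| L (days) | Values of k (of 21) with actual > total | Largest excess (days) |
|---|---|---|
| 0 | 20 | 20 |
| 3 | 17 | 17 |
| 7 | 13 | 13 |
| 14 | 6 | 6 |
| 21 | 0 | none |

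Examples:

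- Death on Day 10 of cycle 1: total 10, actual 21.
- DCO 5 days after an on-schedule second dose (Day 27): total 27, actual 42.
- Doses on Days 1 and 43 with one dose skipped between, DCO on Day 48: total 48, actual 42, so the order is normal.

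**Step 4: no death or DCO within 20 days of the last dose, no early dosing.** Actual is below total: by 1 day if undelayed, and by 22 after one skipped dose (doses on Days 1 and 43: total 43 + 21 − 1 + 1 = 64, actual 42). Of those 22 days, 21 are the skipped cycle and 1 is the overcount.

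**Step 5: early dosing inside the visit windows.** With C2 on Day 21 and C3 on Day 40, total = 40 + 21 − 1 + 1 = 61 and actual = 63. This is a small further route to the same inversion.

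**Step 6: what uses these durations.** Relative dose intensity uses dose amounts up to the last dosing day. The cycle count is a count. DLT evaluability uses the percentage of the first dose received. Treatment-emergent AEs run to 97 days after the last dose or to subsequent therapy (SAP 4.2.1.2). None of them draws on total or actual duration.

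**The case against.** The strongest reply is that this changes nothing that matters. The overcount is the same single day for every uncut participant, shrinks in relative terms with each cycle, and sits in a descriptive study with no statistical comparison between cohorts. Actual duration is defined but not named among the planned outputs, so the inversion may never be printed. Delays and interruptions are summarised directly, as counts with reasons. All of this stands, and it sets the severity.

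It is also right that the inversion is conditional. A reader might infer that anyone who dies or is in a cycle at the DCO has actual above total, or that many participants are affected. Neither is supported. Earlier delays or a skipped dose can restore the normal order, as Step 3 shows, and so can a cut 20 or more days after the last dose. SAP 4.1.1.2 lists a row for participants still on treatment at DCO, but neither document gives a number for that group or for deaths on treatment.

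A reader might further infer that the primary safety rates are distorted. The planned primary summaries are percentages of participants (SAP Table 3), and I find no exposure-adjusted rate in the SAP. Nor does the SAP derive a difference between actual and total duration that could be spoiled.

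What the reply does not remove is that both rules, followed as written, return wrong values: 22 days for a 21-day cycle, and exposure credited after death or after the data end.

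**Conclusion.** Wrong as written; low severity, worth correcting but not blocking.

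- **Total duration** is one day too long for every participant not cut at death or DCO. This is certain given a 21-day cycle and inclusive day counting, and it enters a planned summary.
- **Actual duration** exceeds total when death or DCO falls less than 20 days after the last dose, by up to 20 days, unless earlier delays or skipped doses offset it. Early dosing can add a small inversion of its own.

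The number affected by the second defect is unknown. As an assumed range, it is near 0% if almost everyone is off treatment by the DCO, as may hold at the late final analysis. At an earlier DCO it could reach about 95% (20/21) of undelayed participants still on treatment, if the DCO is equally likely to fall on any day of the cycle. The consequence is confined to descriptive exposure figures.

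**What to change.** Change two formulas in SAP 4.2.1.1.1.

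1. Total duration = min(last dose date + 20, death, DCO) − first dose date + 1. Bring the sentence above the formula into line. Keep the +1: it is right where death or DCO ends the period (death on Day 10 gives 10 − 1 + 1 = 10 days), so deleting it would move the error to those participants.
2. Actual duration = 21 × (cycles − 1) + min(21, earlier of death and DCO − last dose date + 1). This cuts only the last cycle.

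Checks: undelayed and uncut, both give 21, 42, 84 and 126 for 1, 2, 4 and 6 cycles. Death on Day 10 of cycle 1 gives 10 for both. One skipped dose gives total 63 and actual 42, a gap of exactly one cycle.

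The shortcut of taking the smaller of cycles × 21 and total duration should be avoided because it hides real delays. With cycle 2 on Day 36 and death on Day 41, it returns min(42, 41) = 41, whereas the time covered is 21 + 6 = 27, which formula 2 gives.

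Early dosing still leaves a small inversion (the Step 5 example becomes total 60, actual 63), because each earlier cycle is credited with 21 days. A sentence in the SAP acknowledging this is enough.

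The cost is two formula edits and the matching programming. No data collection, analysis set or other endpoint changes.
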